Total	[column total]		[sum of 4 blocks, should be N]			
<<Post Dose One Visit 2>>						
Normal						
Abnormal						
Total						
Continue for all Post Dose One visits						

1. Footnote defines when pre-dose measurement was taken

TABLE 14.3.4.5.x:

Shift Table for <<ordinal-graded laboratory parameter>> by Treatment Group Comparing Pre-Dose One Measure to Post-Dose One Measures <<Overall/Site>>

	CHIKV (N=X) Baseline					Placebo (N=X) Baseline				
Pre-Dose One ¹	Grade 1	Grade 2	Grade 3	Grade 4	Total	Grade 1	Grade 2	Grade 3	Grade 4	Total
Grade 1	x	x	x	x	x	x	x	x	x	x
Grade 2										
Grade 3										
Grade 4										
Total										
Continue for all Post Dose One visits										

1. Footnote defines when pre-dose measurement was taken

TABLE 14.3.5:
Distribution of Vital Signs by Day Post Dosing, Grade, and Treatment Group <<Age Stratum, Overall/Site>>

[Implementation Note: If an assessment has a grading scale that includes grading for both high and low, then include one row for each severity for high and low.]

If data is not collected, enter 'N/A' for entry. (For example, Temperature at Post-Injection)

Repeat this table for Placebo group

Vital Signs Assessment	Severity	Pre-injection (Baseline) CHIKV (N=X)		Post-injection CHIKV (N=X)		Week 4 CHIKV (N=X)		Week 8 CHIKV (N=X)		Week 16 CHIKV (N=X)		Week 24 CHIKV (N=X)		Week 32 CHIKV (N=X)		Week 40 CHIKV (N=X)		Week 48 CHIKV (N=X)		Week 56 CHIKV (N=X)		Week 64 CHIKV (N=X)		Week 72 CHIKV (N=X)		Max Severity Post Baseline CHIKV (N=X)	
		n	%	n	%	n	%	n	%	n	%	n	%	n	%	n	%	n	%	n	%	n	%	n	%	n	%
Any Assessment	Normal	x	x.x	x	x.x	x	x.x	x	x.x	x	x.x	x	x.x	x	x.x	x	x.x	x	x.x	x	x.x	x	x.x	x	x.x	x	x.x
	Mild																										
	Moderate																										
	Severe																										
	Potentially Life Threatening																										
Systolic BP	Normal																										
	Mild																										
	Moderate																										
	Severe																										
	Potentially Life Threatening																										

Vital Signs Assessment	Severity	Pre-injection	Post-injection	Week 4	Week 8	Week 16	Week 24	Week 32	Week 40	Week 48	Week 56	Week 64	Week 72	Max Severity Post Baseline
		(Baseline) CHIKV (N=X)	CHIKV (N=X)	CHIKV (N=X)	CHIKV (N=X)	CHIKV (N=X)	CHIKV (N=X)	CHIKV (N=X)	CHIKV (N=X)	CHIKV (N=X)	CHIKV (N=X)	CHIKV (N=X)	CHIKV (N=X)	CHIKV (N=X)
Diastolic BP	Normal													
	Mild													
	Moderate													
	Severe													
	Potentially Life Threatening													
Pulse	Normal													
	Mild													
	Moderate													
	Severe													
	Potentially Life Threatening													
Temperature (°C)	Normal													
	Mild													
	Moderate													
	Severe													
	Potentially Life Threatening													

TABLE 14.3.6:
Number and Percentage of Subjects with Concurrent Medications by
Treatment Group <<Age Stratum>>

Medication	CHIKV (N=X)		Placebo (N=X)		All Subjects (N=X)	
	n	%	n	%	n	%
	x	x.x	x	x.x	x	x.x

TABLE 14.3.7:
Number of Pregnancies by Outcome and Treatment Group

	CHIKV (N=X)	Placebo (N=X)	All Subjects (N=X)
Total pregnancies	x	x	x
Live births			
Spontaneous abortions			
Elective abortions			
Ectopic pregnancies			
Stillbirths			

TABLE 15.1.1:
Incidence of Clinical Cases of CHIKV Post Dose One by Treatment Group and Stratified by Age

Age Stratum	CHIKV			Placebo		
	n	%	95%CI	n	%	95%CI
18-40	x	xx	xx-xx	x	xx	xx-xx
41-60						
Aggregate (18-60)						

Note: Subjects not receiving dose two are included in this table.
 n = number of subjects with CHIKV symptoms (clinical cases)
 % = n divided by the number of subjects receiving dose one
 95%CI = 95% Clopper-Pearson confidence interval.

TABLE 15.1.2:
Incidence of Clinical Cases of CHIKV Post Dose Two by Treatment Group and Stratified by Age

Age Stratum	CHIKV			Placebo		
	n	%	95%CI	n	%	95%CI
18-40	x	xx	xx-xx	x	xx	xx-xx
41-60						
Aggregate (18-60)						

n = number of subjects with CHIKV symptoms (clinical cases)

% = n divided by the number of subjects receiving dose two and free of infection when receiving dose two

95%CI = 95% Clopper-Pearson confidence interval.

Additional Tables using the same format as 15.1.1 and 15.1.2

TABLE 15.1.3:
Incidence of PCR Confirmed Cases of CHIKV Post Dose One by Group and Stratified by Age

TABLE 15.1.4:
Incidence of PCR Confirmed Cases of CHIKV Post Dose Two by Group and Stratified by Age

TABLE 15.2.1:

Primary Exploratory Analysis – Vaccine Efficacy for Time to Occurrence of Clinical CHIKV Infection Post Dose One

	CHIKV N= Placebo N=		
	V.E.	95% CI for V.E.	p-value
Primary Analysis: Unadjusted	x.xx	xx.xx - xx.xx	x.xxx

N=number of subjects in the specific treatment group that received first dose

V.E. =Vaccine efficacy obtained from Cox Proportional Hazard model

95%CI = 95% confidence interval obtained from Cox Proportional Hazard model

p-value = result of comparison of Kaplan-Meier survival curves between groups by Log-rank test.

TABLE 15.2.2:

Primary Exploratory Analysis – Vaccine Efficacy for Time to Occurrence of Clinical CHIKV Infection Post Dose Two

	CHIKV N= Placebo N=		
	V.E.	95% CI for V.E.	p-value
Primary Analysis: Unadjusted	x.xx	xx.xx - xx.xx	x.xxx

N=number of subjects in the specific treatment group that received **second** dose

V.E. =Vaccine efficacy obtained from Cox Proportional Hazard model

95%CI = 95% confidence interval obtained from Cox Proportional Hazard model

p-value = result of comparison of Kaplan-Meier survival curves between groups by Log-rank test.

Additional Tables using the same format as 15.2.1 and 15.2.2

TABLE 15.2.3:

Primary Exploratory Analysis – Vaccine Efficacy for Time to Occurrence of PCR Confirmed CHIKV Infection Post Dose One

TABLE 15.2.4:

Primary Exploratory Analysis – Vaccine Efficacy for Time to Occurrence of PCR Confirmed CHIKV Infection Post Dose Two

TABLE 15.3.1:

Secondary Exploratory Analysis - Vaccine Efficacy for Time to Occurrence of Clinical CHIKV Infection Post Dose One with Adjustment for Baseline Characteristics

	CHIKV N= Placebo N=		
	V.E.	95% CI for V.E.	p-value
Secondary Analysis: Multivariate adjustment for age, race, site	xx.x	xx.x – xx.x	x.xxx
Univariate Adjustments			
Age (18-40, 41-60)	xx.x	xx.x – xx.x	x.xxx
Race (White/Non-White)	xx.x	xx.x – xx.x	x.xxx
Site (1-6)	xx.x	xx.x – x.xx	x.xxx

N=number of subjects in the specific treatment group that received **first** dose

V.E. =Vaccine efficacy obtained from Cox Proportional Hazard model

95%CI = 95% confidence interval obtained from Cox Proportional Hazard model

p-value = for the multivariate adjustment, it is the result of comparison of Kaplan-Meier survival curves between groups by Log-rank test.

For univariate adjustment, it is the result of comparison of Kaplan-Meier survival curves between groups stratified by the adjusted variables by Log-Rank test.

TABLE 15.3.2:

Secondary Exploratory Analysis - Vaccine Efficacy for Time to Occurrence of Clinical CHIKV Infection Post Dose Two with Adjustment for Baseline Characteristics

	CHIKV N= Placebo N=		
	V.E.	95% CI for V.E.	p-value
Secondary Analysis: Multivariate adjustment for age, race, site	xx.x	xx.x – xx.x	x.xxx
Univariate Adjustments			
Age (18-40, 41-60)	xx.x	xx.x – xx.x	x.xxx
Race (White/Non-White)	xx.x	xx.x – xx.x	x.xxx
Site (1-6)	xx.x	xx.x – x.xx	x.xxx

N=number of subjects in the specific treatment group that received **second** dose

V.E. =Vaccine efficacy obtained from Cox Proportional Hazard model

95%CI = 95% confidence interval obtained from Cox Proportional Hazard model

p-value = for the multivariate adjustment, it is the result of comparison of Kaplan-Meier survival curves between groups by Log-rank test.

For univariate adjustment, it is the result of comparison of Kaplan-Meier survival curves between groups stratified by the adjusted variables by Log-Rank test.

Additional Tables using the same format as 15.3.1 and 15.3.2

TABLE 15.3.3:

Secondary Exploratory Analysis – Vaccine Efficacy for Time to Occurrence of PCR Confirmed CHIKV Infection Post Dose One with Adjustment for Baseline Characteristics

TABLE 15.3.4:

Secondary Exploratory Analysis – Vaccine Efficacy for Time to Occurrence of PCR Confirmed CHIKV Infection Post Dose Two with Adjustment for Baseline Characteristics

Statistical Analysis Plan

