4.1.1. Inclusion Criteria

A subject must meet all of the following criteria:

1. 18 to 60 years old
2. Available for clinical follow-up through Study Week 72
3. Able to provide proof of identity to the satisfaction of the study clinician completing the enrollment process
4. Able and willing to complete the informed consent process
5. Willing to donate blood for sample storage to be used for future research
6. In good general health, with a BMI ≤ 40 , without clinically significant medical history, and has satisfactorily completed screening
7. Physical examination and laboratory results without clinically significant findings within the 56 days prior to enrollment

Laboratory Criteria within 56 days prior to enrollment:

8. Hemoglobin either within institutional normal limits or accompanied by site physician approval as consistent with healthy adult status
9. White blood cells either within institutional normal range or accompanied by site physician approval as consistent with healthy adult status
10. Platelets = 125,000 – 500,000/mm³
11. Alanine aminotransferase (ALT) ≤ 1.25 x upper limit of normal (ULN)
12. Serum creatinine ≤ 1.1 x ULN based on site institutional normal range
13. Negative result on an HIV test that meets local standards for identification of HIV infection
14. Negative result on the CHIKV screening antibody assay.

Criteria applicable to women of childbearing potential:

15. Negative human chorionic gonadotropin pregnancy test (urine or serum) on day of enrollment
16. Agree to use an effective means of birth control from 21 days prior to enrollment through 12 weeks after the last study injection

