8.5. Risks and Benefits

8.5.1. Risks of Blood Collections:

The blood collection procedures are common in routine medical practice. The risks of blood sample collection are minimal and consist of mild discomfort at the sample collection site. The procedure may cause mild pain, bruising, fainting, and, rarely, infection at the site where the blood is taken.

8.5.2. Risks of the CHIKV VLP Vaccine:

In VRC 311, the first human trial in which the CHIKV VLP vaccine was administered to 25 subjects, the local and systemic reactogenicity was no more than mild and none of the subjects reported fever. It is possible that once administered to a larger number of subjects, other potential side effects from injection may be observed similar to those seen with other vaccines. Although not previously observed with the CHIKV VLP vaccine, this includes the possibility of anaphylaxis. With vaccines in general, local reactogenicity may include pain, tenderness, redness or induration of the skin at the injection site and systemic reactogenicity may include fever, chills, muscle aches, joint aches, nausea, headache, and fatigue. These side effects will be monitored, are expected to be short term and may or may not require treatment.

In VRC 311, seven laboratory test AEs (occurring in four participants) were assessed as related to study vaccine based on temporal relationship to vaccination. The AEs included four mild transient alanine aminotransferase increases and two mild and one moderate transient neutropenia. All resolved without clinical sequelae. There was no placebo comparison group in the VRC 311 study. The comparison of AEs in placebo and vaccine recipients in the VRC 704 study should provide a more detailed safety profile for the study vaccine.

8.5.3. Other Risks:

There should be no unusual risks associated with the CHIKV VLP vaccine. The effect of this vaccine on an unborn fetus is unknown. Female subjects of child bearing potential who are heterosexually active will be required to agree to use birth control beginning 21 days prior to enrollment and continuing through 12 weeks after last study injection. Women who are pregnant will be excluded from the study. Children will not be enrolled in this study.

8.5.4. Benefits:

Study participants may have no direct benefit from participation in this study but society may benefit from knowledge gained from research on the donated specimens. This protocol is not designed to provide treatment for any condition.

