Bilirubin – when accompanied by any increase in Liver Function Test increase by factor	1.1 – 1.25 x ULN	1.26 – 1.5 x ULN	1.51 – 1.75 x ULN	> 1.75 x ULN
Bilirubin – when Liver Function Test is normal; increase by factor	1.1 – 1.5 x ULN	1.6 – 2.0 x ULN	2.0 – 3.0 x ULN	> 3.0 x ULN
Cholesterol	201 – 210	211 – 225	> 226	---
Pancreatic enzymes – amylase, lipase	1.1 – 1.5 x ULN	1.6 – 2.0 x ULN	2.1 – 5.0 x ULN	> 5.0 x ULN

* The laboratory values provided in the tables serve as guidelines and are dependent upon institutional normal parameters. Institutional normal reference ranges should be provided to demonstrate that they are appropriate.

** The clinical signs or symptoms associated with laboratory abnormalities might result in characterization of the laboratory abnormalities as Potentially Life Threatening (Grade 4). For example, a low sodium value that falls within a grade 3 parameter (125-129 mEq/L) should be recorded as a grade 4 hyponatremia event if the subject had a new seizure associated with the low sodium value.

***ULN” is the upper limit of the normal range.

Hematology*	Mild (Grade 1)	Moderate (Grade 2)	Severe (Grade 3)	Potentially Life Threatening (Grade 4)
Hemoglobin (Female) - gm/dL	11.0 – 12.0	9.5 – 10.9	8.0 – 9.4	< 8.0
Hemoglobin (Female) decrease from baseline value - gm/dL	not applicable	1.6 – 2.0	2.1 – 5.0	> 5.0
Hemoglobin (Male) - gm/dL	12.5 – 13.5	10.5 – 12.4	8.5 – 10.4	< 8.5
Hemoglobin (Male) decrease from baseline value – gm/dL	not applicable	1.6 – 2.0	2.1 – 5.0	> 5.0
WBC Increase - cell/mm ³	10,800 – 15,000	15,001 – 20,000	20,001 – 25,000	> 25,000
WBC Decrease - cell/mm ³	2,500 – 3,500	1,500 – 2,499	1,000 – 1,499	< 1,000
Lymphocytes Decrease - cell/mm ³	750 – 1,000	500 – 749	250 – 499	< 250
Neutrophils Decrease - cell/mm ³	1,500 – 2,000	1,000 – 1,499	500 – 999	< 500
Eosinophils - cell/mm ³	650 – 1500	1501 - 5000	> 5000	Hypereosinophilic
Platelets Decreased - cell/mm ³	125,000 – 140,000	100,000 – 124,000	25,000 – 99,000	< 25,000
PT – increase by factor (prothrombin time)	1.10 x ULN**	1.11 – 1.20 x ULN	1.21 – 1.25 x ULN	> 1.25 ULN
PTT – increase by factor (partial thromboplastin time)	1.10 – 1.20 x ULN	1.21 – 1.4 x ULN	1.41 – 1.5 x ULN	> 1.5 x ULN
Fibrinogen increase - mg/dL	400 – 500	501 – 600	> 600	--
Fibrinogen decrease - mg/dL	150 – 200	125 – 149	100 – 124	< 100 or associated with gross bleeding or disseminated intravascular coagulation (DIC)

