8.6 Clinical Laboratory Evaluations

Safety laboratory parameters evaluated from serum will include only the liver function test measuring ALT. Hematology parameters include hemoglobin, white blood cells (WBC), red blood cells (RBC), hematocrit, mean corpuscular volume (MCV), platelets, and absolute values for lymphocytes, neutrophils, eosinophils, monocytes and basophils. Sites enter the absolute values for the laboratory parameters and the system calculates percentage values. Laboratory safety evaluations are scheduled at week 4, 8, 16, 24, 32, 40, 48, 56, 64, and 72. Clinical laboratory results by subject will be presented in Listings 16.2.8.1 – 16.2.8.2, Appendix III.

As a note, the lab data for site PRCTRC were initially entered as percentage values but, in June 2016, the site switched to reporting absolute values with their respective units. This caused some discrepancy between calculated values in the database and data collection forms at the site. This could influence precision and will be considered as lab data are reported.

Only results for scheduled routine visits will be included in these analyses. In particular, laboratory results obtained at visits other than Week 4 and 8 for diagnosis of AEs will not be included.

Safety laboratory evaluations will be graded as follows: mild (grade 1), moderate (grade 2), severe (grade 3), or life-threatening (grade 4).

Safety laboratory results will be tabulated for each measure by study visit, treatment group, age stratum and grade (**Table 14.3.4.1, Appendix I**). The mean change from baseline along with 95% CI at each time point measured in the study will be computed (**Table 14.3.4.2, Appendix I**). Boxplots of safety laboratory values will be generated for baseline values and for values measured during the course of the study. Each boxplot will show the 1st quartile, the median, and the 3rd quartile, with values smaller than the 1st quartile or larger than the 3rd quartiles plotted as outliers. If appropriate, horizontal lines representing boundaries for abnormal values will be plotted.

Post dose 1 measures may also be summarized using shift tables to compare baseline and follow-up values (**Tables 14.3.4.4.x – 14.3.4.5.x, Appendix I**). Shift tables may be analyzed using Generalized Estimating Equations to account for the longitudinal nature of these data, as follows:

1) For laboratory parameters with two categories: Normal and abnormal (Binary response)

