Neutrophil	Normal												
	Outside Normal Range												
	Grade 1												
	Grade 2												
	Grade 3												
Lymphocyte	Normal												
	Outside Normal Range												
	Grade 1												
	Grade 2												
	Grade 3												
Monocyte	Normal												
	Outside Normal Range												
	Grade 1												
	Grade 2												
	Grade 3												

Lab. Param	Severity	Baseline CHIKV (N=X)	Week 4 CHIKV (N=X)	Week 8 CHIKV (N=X)	Week 16 CHIKV (N=X)	Week 24 CHIKV (N=X)	Week 32 CHIKV (N=X)	Week 40 CHIKV (N=X)	Week 48 CHIKV (N=X)	Week 56 CHIKV (N=X)	Week 64 CHIKV (N=X)	Week 72 CHIKV (N=X)	Max Severity Post Baseline CHIKV (N=X)
	Grade 4												
Eosinophil	Normal												
	Outside Normal Range												
	Grade 1												
	Grade 2												
	Grade 3												
	Grade 4												
Basophil	Normal												
	Outside Normal Range												
	Grade 1												
	Grade 2												
	Grade 3												
	Grade 4												
Other	Normal												
	Outside Normal Range												
	Grade 1												
	Grade 2												

Lab. Param	Severity	Baseline CHIKV (N=X)	Week 4 CHIKV (N=X)	Week 8 CHIKV (N=X)	Week 16 CHIKV (N=X)	Week 24 CHIKV (N=X)	Week 32 CHIKV (N=X)	Week 40 CHIKV (N=X)	Week 48 CHIKV (N=X)	Week 56 CHIKV (N=X)	Week 64 CHIKV (N=X)	Week 72 CHIKV (N=X)	Max Severity Post Baseline CHIKV (N=X)
	Grade 3												
	Grade 4												

Note: The “Max Post Baseline” column includes the maximum severity experienced by each subject at any time point post baseline, including unscheduled assessments. All subjects will be counted once per symptom by time point at the maximum severity.

TABLE 14.3.4.2:
Laboratory Summary Statistics by Parameter, Study Day, and Treatment Group <<Age Stratum, Overall/Site>>

[Implementation Note: For calculated fields (Mean, SD, Median), decimal place should be the format in which the data were collected + 1 extra place. For Min, Max, decimal place should be in the same format in which the data were collected.]

Repeat this table for the Placebo group

Laboratory Parameter	Statistic	Baseline CHIKV (N=X)	Week 4 CHIKV (N=X)	Week 8 CHIKV (N=X)	Week 16 CHIKV (N=X)	Week 24 CHIKV (N=X)	Week 32 CHIKV (N=X)	Week 40 CHIKV (N=X)	Week 48 CHIKV (N=X)	Week 56 CHIKV (N=X)	Week 64 CHIKV (N=X)	Week 72 CHIKV (N=X)
ALT	N	x										
	Mean	xx.x										
	Standard Deviation	xx.x										
	Median	xx.x										
	Min, Max	xx.x, xx.x										
ALT Change from Baseline	N	N/A	x									

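### Table 14.3.4.1 counts laboratory grades that persist from entry together with new ones, and the SAP makes optional the shift tables that would separate them

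*Combined protocol and SAP*

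**What the plan says.** **Entry (protocol 4.1.1).** ALT may be up to 1.25 x ULN. The platelet criterion is "Platelets = 125,000 – 500,000/mm³". For white cells the rule is "White blood cells either within institutional normal range or accompanied by site physician approval as consistent with healthy adult status", and hemoglobin has a parallel rule; neither has a numeric floor. Neutrophils have no criterion of their own, only the general clause "Physical examination and laboratory results without clinically significant findings within the 56 days prior to enrollment".

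**Grading (protocol Appendix IV).** ALT is Grade 1 from 1.1 to 2.5 x ULN. Platelets are Grade 1 at "125,000 – 140,000", and neutrophils at 1,500 to 2,000. A value inside the institutional normal range is not graded.

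**Summary.** The note to SAP Table 14.3.4.1 says that the Max Severity column "includes the maximum severity experienced by each subject at any time point post baseline". SAP 8.6 has no rule requiring a grade to exceed the baseline grade. Table 14.3.5 (vital signs) has a column with the same title, and protocol 4.1 sets no blood-pressure limit.

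**Shift tables.** Protocol 6.4.2 commits to them. SAP 8.6 says "Post dose 1 measures may also be summarized using shift tables to compare baseline and follow-up values".

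**Phase 1 (protocol 8.5.2).** The related laboratory events were "four mild transient alanine aminotransferase increases and two mild and one moderate transient neutropenia", in four of 25 participants, with no placebo group.

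**The concern.** A subject who enters with ALT at 1.2 x ULN and stays there appears in the Max Severity column as a Grade 1 post-baseline result. So does a subject who was normal and rose to 1.2 x ULN after injection. The column cannot tell them apart.

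Laboratory safety is part of the primary endpoint, and Phase 1 had no control group. Six of its seven related laboratory events (four ALT, two neutropenia) were mild, the grade at which the entry and grading bands overlap. Persisting entry grades add a common background to both arms. That makes a modest excess of new mild abnormalities in the vaccine arm harder to see.

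**Working it through.** **Inputs from the documents.** 180 evaluable subjects per arm (200 less the assumed 10% loss), two-sided 5%, Fisher's exact test (protocol 6.3.1, SAP 5.1), and the bands listed above. **Inputs that are assumptions.** The share *b* of each arm graded at baseline and still graded later, and the new-onset rates. The documents give neither.

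**1. The plan's own figure.** SAP Table 3 states 80% power for 1.0% vs 7.5%. The two-proportion formula, with mean rate 0.0425, gives

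n = [1.960·√(2·0.0425·0.9575) + 0.842·√(0.01·0.99 + 0.075·0.925)]² / 0.065² = 150.0

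The continuity correction gives

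n = (150.0/4)·[1 + √(1 + 4/(150.0·0.065))]² = 179.5, that is 180.

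The figure reproduces. Exact Fisher power at 180 per arm is 85%, so the table is slightly conservative. It also shows why background matters: raising the lower rate from 1% to 5% raises the detectable difference from 6.5 to 9.2 points.

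**2. Where the bands overlap.**
- ALT: 1.1 to 1.25 x ULN is both eligible and Grade 1. It lies above normal, so it is always graded. Grade 2 starts at 2.6 x ULN, outside the entry limit.
- Platelets: 125,000 to 140,000 is eligible, and Grade 1 only if outside the institutional normal range. Grade 2 lies below the entry floor.
- Hemoglobin and white cells: graded values can enter with physician approval.
- Neutrophils: graded values can enter if not judged clinically significant.

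**3. What the overlap does to the column.** With new-onset rate *p*, the rate shown is *q = b + (1 − b)p*. At *b* = 5%, placebo is 0.05 + 0.95·0.01 = 5.95% and vaccine is 0.05 + 0.95·0.075 = 12.1%. The difference is (1 − b)·6.5 points. The last column of the table counts only subjects ungraded at baseline, (1 − b)·180 per arm. It approximates what a worsened-from-baseline count would keep.

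| b | Placebo | Vaccine | Difference (points) | Ratio | Power, column as written | Power, ungraded at baseline only |
|---|---|---|---|---|---|---|
| 0 | 1.0% | 7.5% | 6.5 | 7.5 | 85% | 85% |
| 1% | 2.0% | 8.4% | 6.4 | 4.2 | 75% | 85% |
| 2.5% | 3.5% | 9.8% | 6.3 | 2.8 | 61% | 84% |
| 5% | 6.0% | 12.1% | 6.2 | 2.0 | 46% | 83% |
| 10% | 10.9% | 16.8% | 5.9 | 1.5 | 31% | 80% |
| 20% | 20.8% | 26.0% | 5.2 | 1.25 | 18% | 74% |

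If only half of the entry grades persist, read the row for *b*/2. For new-onset rates of 1% vs 6%, the ratio goes from 6.0 to 1.8 and 1.4 at *b* = 5% and 10%, and the difference from 5.0 to 4.75 and 4.5 points. For a large effect (1% vs 16%), power stays at 98% and 91%.

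**4. Whether another planned output counts worsening.**
- The Baseline column of Table 14.3.4.1 gives the number graded, not which subjects moved.
- Mean change with 95% CI (Table 14.3.4.2) can hide a rise in a few subjects.
- The listings trace individuals but give no count by arm.
- The binary shift shell (14.3.4.4.x) shows Normal to Abnormal, but not Grade 1 to Grade 2.
- The ordinal shift shell (14.3.4.5.x) has Grades 1 to 4 and no Normal level, so it cannot show Normal to Grade 1.
- Both shift shells are optional in SAP 8.6.

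**The case against.** The strongest reply is that the plan already makes its main laboratory comparison against baseline, through adverse events. Protocol 5.1.1 includes abnormal laboratory findings among AEs, and the Schedule of Evaluations makes Day 0 the baseline for judging them. SAP 8.3.2 then compares unsolicited AEs between arms by preferred term with Fisher's test. The Phase 1 signals were recorded this way, and protocol 8.5.2 names the AE comparison as the follow-up. The protocol also commits to shift tables. Table 14.3.4.1 has its own Baseline column, so it does not ignore baseline.

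Most of this stands and limits the point. But an AE record depends on site entry, and the documents give no rule tying each rise in laboratory grade to one. The AE tables are therefore not a derived count of worsened grades. The protocol's commitment to shift tables is softened by the document that governs the outputs.

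A reader might go further in four ways that the documents do not support.
- *The column biases the comparison toward one arm.* Randomization spreads entry grades over both arms in expectation; the effect is noise.
- *The trial loses the power shown above.* No test, interval or p-value is planned on this column, and nothing makes it the basis of the safety conclusion. The power figures only illustrate how hard the contrast would be to see.
- *Subjects can enter with Grade 2 ALT or platelets.* Those screening limits reach Grade 1 only. Higher grades are conceivable only for hemoglobin, white cells and neutrophils, subject to the clinical-significance clause.
- *Dilution is substantial.* These are screened healthy adults, the eligible ALT strip is narrow, and values inside the normal range are not graded. Prevalence could be low.

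**Conclusion.** The point holds as a reporting gap, not as an error in a primary analysis. The entry and grading bands overlap, and the Max Severity column counts a persisting entry grade in the same way as a new one. No output that the SAP commits to counts by arm the subjects whose laboratory grade rose.

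The effect is non-directional and mainly shrinks the ratio. It is visible at *b* = 1% (7.5 to 4.2) and large at 5% (2.0), while the absolute difference loses only the fraction *b*. These sizes rest on assumed prevalence, full persistence and assumed new-onset rates. What the documents establish without assumptions is the overlap, the missing baseline condition, the *will*/*may* mismatch on shift tables, and the missing Normal level in the ordinal shell. The same missing condition applies to vital signs in Table 14.3.5, where Phase 1 gives no particular signal.

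**What to change.** 1. In Tables 14.3.4.1 and 14.3.5, add a by-arm column: worsened from baseline, meaning the maximum post-baseline grade is higher than the baseline grade as defined in SAP 3.3. Show subjects with a missing baseline separately. Use this column when describing post-vaccination abnormalities, and keep the existing one as supportive. State whether unscheduled assessments count: the table note includes them, while SAP 8.6 restricts the analyses to scheduled visits.
2. Change *may* to *will* for the shift tables in SAP 8.6, in line with protocol 6.4.2.
3. Add a Normal (Grade 0) level to Table 14.3.4.5.x and its model. That makes five levels and so four cut-points. The model is now written for three categories with two intercepts.

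The cost is one derived flag from data already collected, extra columns, and a row for missing baselines. Trial conduct does not change.
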